#### 6.8.3 Tipping Point Analysis

A sensitivity analysis for the handling of missing data for the primary efficacy endpoint will be carried out using a tipping point analysis. Specifically, a range of response rates for both groups will be explored to determine the tipping point(s) at which the combinations result in no longer reaching statistical significance.

### 6.9 Safety Evaluation

### **6.9.1** Extent of Exposure

The extent of exposure to study drug in each treatment group will be summarized by days with exposure and total number of tablets used.

A subject will be considered compliant with the dosing regimen if the subject takes 80% to 120% of the expected number of doses while enrolled in the study. Total number of days of exposure will be computed as follows:

```
Total Exposure = Date of Last Dose – Date of First Dose + 1

Total Doses = (Date of Last Dose – Date of First Dose + 1 + 2)

– Missed Doses + Extra Doses
```

Treatment compliance will be based on the expected number of doses given the treatment period duration. The number of expected doses will be computed from the Baseline/Day 1 visit date and the Week 10 visit date. If a subject does not have a Week 10 visit, the number of expected doses will be calculated based on end of treatment period date given available information (e.g., date of last dose, last completed visit date).

```
Expected Doses = End of Treatment Period Date – Day 1 Date + 2
```

If the subject is documented as dosing on the End of Treatment Period Date, a dose will be added to the Expected Doses. To allow for the +7 day window around Week 10 that is used for defining PP population, if the number of expected doses exceeds 80, the number of expected doses will be considered 80 doses.

Percent compliance will be calculated from total number of doses and total number of expected doses as follows:

```
Percent Compliance = 100*(Total Doses/Expected Doses).
```

Percent compliance will not be calculated for subjects who are lost to follow-up during the treatment period.

#### **6.9.2** Adverse Events

The incidence of all AEs and TEAEs will be tabulated by treatment received. These AEs will be classified by system organ class and preferred term using MedDRA. For incidence reporting, if a subject reported more than one AE that was coded to the same system organ class or preferred term, the subject will be counted only once for the specific system organ class or preferred term. An overview of AEs, which includes subject incidence of AEs, treatment-related AEs, AEs by severity, SAEs, deaths, and AEs leading to discontinuation, will be presented.

SAEs will be listed and summarized in a similar manner to AEs.

### 6.9.3 Clinical Laboratory Evaluation

Clinical safety laboratory values will be measured by a central laboratory. Summary statistics for actual values and for changes from baseline will be tabulated for laboratory results by scheduled visit.

Subjects with clinical laboratory values outside of the normal reference range at any post-baseline assessment will be summarized. Shifts from baseline laboratory values will be tabulated, with the exception of most reproductive endocrinology laboratory values.

Serum follicle-stimulating hormone, luteinizing hormone, estradiol, progesterone and antimullerian hormone will be summarized separately for women using hormonal contraception/therapies and those not using hormonal contraception/therapies.

By-subject listings of all laboratory data, as well as abnormal laboratory results, will be presented.

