1.5 Serlopitant

1.5.1 Serlopitant Background and Nonclinical Summary

Serlopitant is a small molecule, highly selective NK₁-R antagonist that is administered orally and metabolized by cytochrome P-450 3A4 (CYP3A4), with a plasma half-life of 45-86 hours. It binds with high affinity to the human NK₁-R with a dissociation constant (K_d) of 46 pM; displacing SP binding with a half-maximal inhibition concentration (IC₅₀) of 61 pM. Serlopitant is a potent functional antagonist of SP-induced inositol phosphate generation.

Serlopitant has been extensively studied in animal toxicology studies, including chronic toxicology and carcinogenicity studies. In non-clinical chronic toxicology studies in rats, mice and dogs, treatment related findings of potential clinical significance included increased salivation, decreased body weight gain and food consumption, slight changes in hematology and serum biochemistry parameters, mild increases in liver weight and mild histomorphologic changes. The histomorphologic changes were seen only in rats (not in dogs or mice) and included: very slight ovarian interstitial cell hypertrophy, mammary gland and uterine atrophy; decreased corpora lutea; increased histiocytes in lung and mesenteric lymph nodes; slight skeletal and cardiac muscle degeneration; slight increased hematopoiesis in bone marrow; and slight to moderate vacuolation in kidney tubules. These nonclinical findings occurred at systemic exposures exceeding those anticipated to provide efficacy of serlopitant for pruritus indications in humans (1 to 5 mg tablet daily). No cardiac lesions have been observed in dog toxicity studies up to 9 months in duration nor in a 3-month mouse range-finding study and 2-year mouse carcinogenicity study at exposure higher than the lowest level which caused cardiotoxicity in rats. The no observed adverse effect level (NOAEL) in rats for histomorphological changes in the reproductive tract, mammary gland and bone marrow provides a 2.5-fold margin for the maximum-targeted exposure (5 mg tablet daily). The rat NOAEL for histomorphological changes in muscle and kidney provides a 5-fold margin for the maximum-targeted exposure (5 mg tablet daily).

In summary, the nonclinical toxicity noted with serlopitant provides no contraindications to the continuation of clinical trials via the oral route. Findings in the developmental toxicity

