6.2.1 Vital Signs

Vital signs will include measurements of heart rate, blood pressure, respiration rate, and temperature after the subject has been calmly resting (seated or supine) for a minimum of 5 minutes. Vital signs will be assessed as outlined in [Appendix A](#) and at unscheduled study visits when clinically indicated. On study visits when clinical laboratory tests are performed, assessment of vital signs should precede blood draw.

6.2.2 *Physical Examination*

Physical examinations, including height and weight measurements, will be performed as outlined in [Appendix A](#) and at unscheduled study visits when clinically indicated. A complete physical examination will be performed at the screening visit, while subsequent examinations will be abbreviated and targeted to changes in disease activity and/or subjects' symptoms. For female subjects with targeted breast examinations, please perform breast examination after blood draw for clinical laboratory tests.

6.2.3 *Clinical Laboratory Assessments*

Samples for clinical laboratory assessments will be collected as outlined in [Appendix A](#) and at unscheduled study visits when clinically indicated, and analyzed at a central laboratory unless otherwise specified.

Detailed instructions regarding sample collection, preparation, and shipment can be found in the laboratory manual. Laboratory assessments will include the following, and are ideally performed in the morning, particularly at visits with endocrine assessments (Screening, Week 10, Follow-up):

- Hematology: hematocrit, hemoglobin, red blood cell count, red blood cell indices, platelets, white blood cell count, white blood cell differential (neutrophils, lymphocytes, monocytes, basophils, eosinophils)
- Chemistry: sodium, potassium, chloride, bicarbonate, glucose, blood urea nitrogen, creatinine, calcium, phosphorus, magnesium, albumin, uric acid, total protein, ALT, AST, alkaline phosphatase, total bilirubin, lactate dehydrogenase (LDH), lipid panel
- Iron studies: ferritin, serum iron
- Serology: hepatitis B and C serology, HIV
- Serum IgE
- Pregnancy testing: all females of childbearing potential will have a local urine pregnancy test performed. Positive or equivocal urine pregnancy test results will be confirmed by a serum pregnancy test analyzed at a central laboratory
- Endocrine: TSH, free T4, cortisol, corticotropin (adrenocorticotrophic hormone, ACTH), prolactin

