- Reproductive endocrinology (for all female subjects under 55 years of age at consent): serum follicle-stimulating hormone (FSH), luteinizing hormone (LH), estradiol, progesterone, anti-Mullerian hormone (AMH)
- Optional study provided in lab test kits for use at Screening only: endomysial antibody with reflex to titer for subjects with signs or symptoms of dermatitis herpetiformis

- Additional optional studies will be supported through local procedural and/or laboratory assessments, including, but not limited to, skin biopsy and pathology interpretation, urea breath test for *Helicobacter pylori*, and allergy testing (patch, prick, or blood testing); the investigator should discuss the need for such studies with the medical monitor during the Screening period.
- Standard cosyntropin stimulation testing should be performed on subjects with low cortisol level (i.e. < 3.0 mcg/dL); the investigator should discuss low cortisol (and relevant low corticotropin) results with the medical monitor.

6.2.4 *Electrocardiogram*

A standard 12-lead ECG will be performed after the subject has been calmly resting in a supine position for a minimum of 5 minutes before obtaining the ECG. ECGs should precede measurement of vital signs and blood draw for clinical laboratory tests and will be performed as outlined in [Appendix A](#) and at unscheduled study visits when clinically indicated and read centrally. ECG machine and detailed instructions will be provided by the ECG vendor.

6.2.5 *Hospital Anxiety and Depression Scale*

The HADS is a QOL instrument designed to assess the severity of anxiety and depression over the prior week, developed in a hospital outpatient clinic, but also valid in community settings and primary care medical practice. The questionnaire takes approximately 2 to 5 minutes to complete, and is provided in [Appendix F](#). The HADS questionnaire will be collected as outlined in [Appendix A](#).

6.2.6 *Epworth Sleepiness Scale*

The ESS is a QOL instrument intended to measure daytime sleepiness by use of a very short questionnaire. The questionnaire takes approximately 2 to 3 minutes to complete, and is provided in [Appendix G](#). The ESS questionnaire will be collected as outlined in [Appendix A](#).

6.2.7 *Assessment of Potential for Physical Dependence*

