#### **6.9.4.4 Menstrual Diaries**

Menstrual diary dates will be used to summarize number and duration of menses.

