ANL	xx ( xx.x%)	xx ( xx.x%)	xx ( xx.x%)	xx ( xx.x%)	xx ( xx.x%)	xx ( xx.x%)

Note: BNL=Below Normal Limit, WNL=Within Normal Limits, ANL=Above Normal Limit.

No imputation of missing values. Baseline is the latest recorded value prior to first dose of study drug. "Latest Follow-up" visit includes the latest available follow-up information for each subject from the 3-Week or 5-Week Follow-up visits.

SOURCE: USERNAME\SPONSOR\PROJECT\JOBNAME (DATE,TIME)

Table to include following lab tests: "TSH ULTRASENSITIVE", "THYROXINE, FREE", "CORTISOL, SERUM RANDOM", "ACTH, PLASMA", "ANTI-MULLERIAN HORMONE".

Statistical Analysis Plan for Menlo Therapeutics Inc. Protocol Number: MTI-105

Table 14.3.1.5.1.1: Summary of Treatment-Emergent Electrocardiogram (ECG) Parameter Abnormalities (Safety Population)
(Page 1 of 2)

	Placebo	Serlopitant 5 mg
	(N=xxx)	(N=xxx)
number of Subjects with Treatment-Emergent ECG esults	XXX	XXX
R Interval		
> 200 msec	xx ( xx.x%)	xx ( xx.x%)
> 220 msec	xx ( xx.x%)	xx ( xx.x%)
hange from Baseline in PR Interval		
>= 25% and > 200 msec	xx ( xx.x%)	xx ( xx.x%)
RS Interval		
> 110 msec	xx ( xx.x%)	XX (XX.X%)
> 120 msec	xx ( xx.x%)	xx ( xx.x%)
hange from Baseline in QRS Interval		
>= 25% and > 110 msec	xx ( xx.x%)	xx (xx.x%)
>= 25% and > 120 msec	xx ( xx.x%)	xx ( xx.x%)
TcF Interval		
> 450 - 470 msec	xx ( xx.x%)	xx (xx.x%)
> 470 - 500 msec	xx ( xx.x%)	XX (XX.X%)
> 500 msec	xx ( xx.x%)	xx ( xx.x%)
hange from Baseline in QTcF Interval		
> 30 - 60 msec	xx ( xx.x%)	xx (xx.x%)
> 60 msec	xx ( xx.x%)	XX (XX.X%)
	,	,
TcF Interval > 500 msec and Change from Baseline > 60	xx ( xx.x%)	xx ( xx.x%)
sec		

Note: No imputation of missing values. Baseline is the latest recorded value prior to first dose of study drug. Change calculated as post-baseline – baseline. SOURCE: USERNAME\SPONSOR\PROJECT\JOBNAME (DATE,TIME)

Statistical Analysis Plan for Menlo Therapeutics Inc. Protocol Number: MTI-105

Table 14.3.1.5.1.1: Summary of Treatment-Emergent Electrocardiogram (ECG) Abnormalities (Safety Population)
(Page 2 of 2)

	Placebo (N=xxx)	Serlopitant 5 mg (N=xxx)
Number of Subjects with Treatment-Emergent ECG Results	xxx	xxx
QTcB Interval		
> 450 - 470 msec	xx ( xx.x%)	xx (xx.x%)
> 470 - 500 msec	xx ( xx.x%)	xx ( xx.x%)
> 500 msec	xx ( xx.x%)	xx ( xx.x%)
Change from Baseline in QTcB Interval		
> 30 - 60 msec	xx ( xx.x%)	xx (xx.x%)
> 60 msec	xx ( xx.x%)	xx ( xx.x%)
QTcB Interval > 500 msec and Change from Baseline > 60 msec	xx ( xx.x%)	xx ( xx.x%)

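### The planned summaries of reproductive hormones and menses are insensitive to a moderate ovarian effect

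*SAP*

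**What the plan says.** Protocol 6.2.3 orders the reproductive panel "for all female subjects under 55 years of age at consent", at Screening, Week 10 and Follow-up. The only timing rule is the hour: laboratory tests "are ideally performed in the morning, particularly at visits with endocrine assessments (Screening, Week 10, Follow-up"). No cycle day is set.

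SAP 6.9.3 then says the five hormones "will be summarized separately for women using hormonal contraception/therapies and those not using hormonal contraception/therapies". Table 14.3.1.4.3.1.1 pools all sampled women, users included; the next two tables give users and non-users. Each shell shows n, mean, SD, median and range, for observed values and for change from baseline. None separates menstruating from non-menstruating women. The same section adds: "Shifts from baseline laboratory values will be tabulated, with the exception of most reproductive endocrinology laboratory values". The note under Table 14.3.1.4.3.2 keeps only "ANTI-MULLERIAN HORMONE" from this panel.

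Women who report periodic menstruation keep a paper diary throughout the study (Protocol 6.5). SAP 6.9.4.4 says: "Menstrual diary dates will be used to summarize number and duration of menses". The shell of Table 14.3.1.10 has one block for number and one for duration in each arm, with no study periods and no rate. SAP 6.9.4.4 refers to the duration of menses, while the shell labels the row as duration of menstrual cycles. Those are different quantities.

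**The concern.** Protocol 1.5.1 reports, in rats, "very slight ovarian interstitial cell hypertrophy, mammary gland and uterine atrophy; decreased corpora lutea". It gives a 2.5-fold exposure margin for the reproductive-tract changes at the trial dose. Against that background, a reader will look to the hormone and menses tables for any sign of disturbed ovarian function.

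Progesterone, LH, FSH and estradiol depend on cycle phase. If the phase of each draw is arbitrary, much of the spread in the change scores is phase. Women who do not menstruate have no cycle to lose, so they pull the mean shift towards zero. A menses count that mixes drug-free time with treatment time blunts any on-drug effect, and it falls when a woman leaves early for any reason. A table showing no difference could then be read as more reassuring than it is.

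**Working it through.** **Inputs.** The documents give no sample size, power or error rate for these readouts, so there is no planned figure to reproduce. Safety summaries are descriptive; z and power below are yardsticks only. From the protocol: Screening to Baseline is 14 to 31 days, Week 10 is Day 70 ± 7, and Follow-up is 35 to 38 days after Week 10. Assumed: cycle lengths, 10 to 30 cycling non-users per arm, and luteal shares.

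**1. Is phase at Week 10 tied to phase at Screening?** The gap runs from 14 + 63 = 77 days to 31 + 77 = 108 days, a spread of 31 days. That exceeds an assumed 28-day cycle and is 31/35 = 89% of a 35-day cycle. Phase at the two draws is effectively unrelated.

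**2. Hormone tables.** Suppose half the draws are luteal, luteal progesterone is R times follicular, and a fraction f of treated women stop ovulating.
- Mean shift: f(R−1)/2.
- SD of one observed value: (R−1)/2, so the standardized effect is d = f.
- SD of a change: (R−1)/√2, so d = f/√2 = 0.71f.
- z = d√(n/2), with the no-effect SD in both arms.

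| f | n per arm | z, change | z, observed Week 10 value |
|---|---|---|---|
| 30% | 10 / 20 / 30 | 0.47 / 0.67 / 0.82 | 0.67 / 0.95 / 1.16 |
| 50% | 10 / 20 / 30 | 0.79 / 1.12 / 1.37 | 1.12 / 1.58 / 1.94 |
| 100% | 10 / 20 / 30 | 1.58 / 2.24 / 2.74 | 2.24 / 3.16 / 3.87 |

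If a share m of the non-users does not menstruate and their values do not move, the group's mean shift shrinks by the factor 1−m.

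A second model compares the share of luteal-range samples, q against q(1−f), with q = 0.4 to 0.5 (two-sided 5% chi-squared). At f = 50%, power is 16–20%, 28–37% and 39–52% for 10, 20 and 30 per arm. At f = 100% it is 63–78% for 10 and 92–98% for 20.

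**3. Menses count.** A completer's diary runs from 14 + 63 + 35 = 112 to 31 + 77 + 38 = 146 days. The on-drug share s is lowest at 63/(31 + 63 + 38) = 63/132 = 0.477 and highest at 77/(14 + 77 + 35) = 77/126 = 0.611. If the drug multiplies the on-drug rate by r, the whole-study ratio to placebo is 1 − s(1−r).
- r = 0.5: 1 − 0.611 × 0.5 = 0.69 to 1 − 0.477 × 0.5 = 0.76, against a true on-drug ratio of 0.50.
- r = 0: 0.39 to 0.52, against 0.

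**4. Early exit.** Take 14 days of screening. A completer has 14 + 70 + 35 = 119 days, or 4.25 menses at 28 days. A woman who stops drug on Day 35 and completes the 5-week follow-up has 14 + 35 + 35 = 84 days, or 3.0 menses with an unchanged cycle. The ratio is 84/119 = 0.71. For a completer on the same schedule, a halved on-drug rate gives (14 + 35 + 35)/119 = 0.71 as well. The table cannot tell the two apart.

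**The case against.** The case against is substantial. Randomization balances phase and menopausal status in expectation, so ignoring them does not bias the hormone comparison. The shells already print observed Week 10 values, which under the model above are more sensitive than change. Anti-Mullerian hormone is summarized and keeps its shift table. Out-of-range values are summarized. Dated laboratory and diary listings, with childbearing potential, allow a subject-level check. Abnormal bleeding is asked about at visits and can reach the adverse event tables. The histomorphologic changes were seen only in rats, at exposures above those anticipated for efficacy. No objective or endpoint assigns these data the task of detecting loss of ovulation. The affected subgroup is probably small: Protocol 1.1 puts the median prevalence age in the 50s and 60s.

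Most of this stands, and it limits the point to sensitivity. Three things remain. A listing shows that a better summary is feasible but does not pre-specify one. Bleeding queries need not pick up cycles without ovulation. And randomization does not protect the menses count, because time observed is determined after randomization.

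There is also a fair warning about remedies. Dating the Week 10 sample by counting back from the next onset would leave unassigned exactly those women whose menses stop on drug, and so would exclude more treated women if the drug acts.

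**Conclusion.** The point holds as one of sensitivity. Under the assumptions above, the hormone tables would probably miss an effect in 30% to 50% of cycling women. The menses count would show a halved on-drug rate as roughly 0.69 to 0.76, and it is open to bias from unequal early exit.

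A reader might infer that the tables cannot show an ovarian effect at all, or that a null table carries almost no information. The documents do not support that: complete suppression gives z = 2.24 on change and 3.16 on observed values at an assumed 20 per arm, and anti-Mullerian hormone is handled separately. A reader might also infer that the hormones and diary are there to detect loss of ovulation. That is a natural inference from the rat findings, but the protocol does not say it. Likewise, SAP 6.9.4.4 names no period for the menses count; whole-study coverage is inferred.

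Subgroup sizes, luteal shares and cycle lengths are assumptions. No primary or key secondary efficacy result is touched.

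**What to change.** Before unblinding:

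1. In SAP 6.9.3 and Table 14.3.1.4.3.1.3, split non-users by baseline status only: childbearing potential and periodic menstruation reported at Screening. Remove FSH, LH, estradiol and progesterone from the pooled Table 14.3.1.4.3.1.1.
2. In Table 14.3.1.10, report menses per 28 days observed, separately for screening, on-drug and post-drug time. State whether the duration row means length of bleeding, as SAP 6.9.4.4 implies, or start-to-start cycle length.
3. If cycle phase is shown, label it supportive. Date each sample by days since the last recorded onset, and show women with no later onset as their own category by arm instead of excluding them.

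The cost is SAP text, revised shells and some date programming, with no new samples or visits. Cells become smaller. The gain is in interpretation, not proof: 3 low values of 10 against 0 of 10 gives a two-sided Fisher p of 2 × C(10,3)/C(20,3) = 2 × 120/1140 = 0.21.

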### 6.9.4 Other Observations Related to Safety

#### **6.9.4.1 ECG Measurements**

Summary statistics for actual values and for changes from baseline will be tabulated for ECG parameter results by scheduled visit. The overall ECG assessment (abnormal or normal) will be summarized along with a summary of how many subjects developed a post treatment abnormal result. The study relevance of the finding (i.e. clinical significance as determined by the investigator) will be provided in a by-subject listing.

### 6.9.4.2 Vital Signs

The observed data and change from baseline for each measurement day will be summarized with descriptive statistics, as well as provided in a by-subject listing.

### 6.9.4.3 Physical Exams

Clinically significant physical exam findings will be recorded by the sites within medical history or adverse events and otherwise not summarized.

#### **6.9.4.4 Menstrual Diaries**

Menstrual diary dates will be used to summarize number and duration of menses.

### 6.9.4.5 Hospital Anxiety and Depression Scale (HADS)

The observed data and change from baseline for the HADS will be summarized with descriptive statistics by scheduled visit. Both the Depression and Anxiety subscales will be reported.

## 6.9.4.6 Epworth Sleepiness Scale (ESS)

The observed data and change from baseline for the ESS will be summarized with descriptive statistics by scheduled visit.

### 6.9.4.7 Potential for Physical Dependence

In order to assess physical dependence and withdrawal, data collected during a 5-week post-drug observation period will be summarized. For each assessment, an on-drug baseline value is defined as Week 10 (for subjects completing treatment) or the last observation prior to last dose of study drug (for subjects that discontinued treatment early).

The observed data and change from on-drug baseline for the HADS will be summarized with descriptive statistics by time point (3-Day Follow-up, and 1-, 2-, 3-, 4- and 5-Week Follow-up). Both the Depression and the Anxiety subscales will be reported.

The observed data and change from on-drug baseline for the ESS will be summarized with descriptive statistics by time point (3-Day Follow-up, and 1-, 2-, 3-, 4- and 5-Week Follow-up).

Vital signs including change from on-drug baseline will be summarized with descriptive statistics for each post-study drug observation visit.

Overall ECG assessments (abnormal or normal), as well as observed and change from on-drug baseline for ECG parameters, will be summarized for the 5-week post-study drug visit. In addition, a summary of how many subjects developed a post-drug abnormal result will be presented.

Assessment of AEs reported after study drug discontinuation, i.e. during the post-study drug observation period, will be summarized separately by treatment group. AEs during the post-study drug observation period will be summarized by weekly periods and sex.

